Declines in adequate protein and calorie intake results in accelerated loss of muscle mass and physical functioning in older adults.¹⁸⁻²⁰ Prior randomized trials demonstrate that increased protein intake coupled with resistance training, is the most effective strategy to improve physical function.^{19,21,8,22-25} Despite substantial evidence, there is a paucity of research on protein consumption and resistance training among OCS, a population at high risk for functional limitations. Given the ongoing COVID-19 pandemic and the positive impact of online behavior change interventions for cancer survivors,²⁶⁻³⁴ online-based interventions to improve physical function should be tested among OCS. A novel approach to improving physical function in OCS is to utilize online, tailored education and counseling from registered dietitians and exercise scientists, to improve dietary intake (protein intake, diet quality) and participation in resistance exercise. The proposed study will be the first synchronous, online protein-focused diet and resistance training intervention among OCS.

SPECIFIC AIMS

Our objective is to improve physical function through online, tailored nutritional and resistance training counseling to increase protein intake, improve diet quality, increase resistance training, and improve health outcomes (muscle strength, dietary quality, HRQoL, self-efficacy, weight management). This online delivery mechanism also decreases participant exposure to COVID-19 among susceptible OCS. We will utilize established strategies to improve physical function in an innovative way through a 12-week synchronous, online counseling and education intervention for OCS at high risk for physical function impairment. Recruitment will take place at The Ohio State University Comprehensive Cancer Center. Our rationale is that understanding the influence of nutritional and resistance training counseling and education among OCS is likely to advance the science of geriatrics and cancer survivorship. This study, the E-PROOF (**E**-intervention for **P**rotein **I**ntake and **R**esistance **T**raining **to** **O**ptimize **F**unction) study, builds on our team's expertise in geriatrics, cancer survivorship, diet, exercise, and physical function and our preliminary data on the dietary, exercise, and physical function deficits among OCS. To attain the overall objective, two aims will be pursued:

Aim 1: Determine the feasibility and acceptability of implementing a 12-week online dietary and resistance training randomized trial with 70 older cancer survivors. This aim will be accomplished by collecting detailed process data, which allows the assessment of accrual, retention, and adherence. Our hypothesis is that we will recruit (within 9 months) 70 OCS, retain $\geq 80\%$ of the sample, and maintain $\geq 80\%$ adherence to the intervention.

Aim 2: Examine the preliminary efficacy of this 12-week online dietary and resistance training intervention with the intervention participants. Registered dietitians and exercise scientists will provide these participants with tailored dietary and resistance training recommendations, counseling, and educational materials. Our hypothesis is that intervention participants will experience statistically significant, clinically meaningful improvements in physical function and associated health outcomes (i.e., muscle strength, dietary quality, HRQoL, self-efficacy,

weight management) after the 12-week dietary and resistance training intervention and at a 3-month post-intervention follow-up.

METHODS

I. STUDY DESIGN

We will examine the feasibility and preliminary efficacy of a 12-week online dietary and resistance training intervention to improve the physical function of OCS through increased protein consumption, healthy eating, and resistance training. In this pilot randomized controlled trial, participants (n=70) will be randomized to one of the two groups: experimental (online counseling, menus, educational materials) and enhanced control (passive educational materials). We will examine the intervention effects on physical function and associated health outcomes during the 12-week period between the experimental and control group.

II. PARTICIPANT SELECTION

1. *ELIGIBILITY CRITERIA*

Eligibility criteria are: ≥ 65 years of age, a primary diagnosis of stage I-III breast, colorectal, and prostate cancer, completion of primary curative treatment, reported at least 1 physical function limitation on the PFSS ("limited a little", "limited a lot"), no evidence of progressive disease or second cancers, community-dwelling, and able to provide consent. The 3 cancer types are chosen because they are the most common cancer types³⁵ with high 5-year survival rates.³⁶ Additionally, most of the evidence of the benefits of exercise and diet has occurred in survivors diagnosed with breast, prostate, or colorectal cancer.^{24,37-39} Individuals are excluded if they currently receive cancer treatment (e.g., chemotherapy, radiation), have liver and/or renal disease limiting their protein intake, are under the care of a RD/nutritionist, participating in other diet/exercise interventions, consume protein supplements, and have contraindications to unsupervised exercise (e.g., walker/wheelchair use).

2. *RECRUITMENT*

Five methods will be employed to recruit potential participants:

1. Flyers distributed at the JamesCare for Life programs (wellness programs offered through the Ohio State University Comprehensive Cancer Center (OSUCCC)) as well as through their email list of cancer survivors. Flyers will also be distributed at the OSUCCC's Cancer and Aging Resiliency (CARE) clinics, multidisciplinary clinics designed to address the unique needs of older cancer survivors, and the OSUCCC GI Medical Oncology Clinic. The study will be advertised on the flyer and eligible women and men will be requested to contact the research assistant if they are interested in study participation.

2. In-person during follow-up visits at the Survivorship Clinic and CARE clinics within OSUCCC by study team member ([name]). When prospective patients are identified, the provider will provide the prospective participant with the recruitment flyer that has the PI and research assistant's names and contact information. In addition, the research assistant will be in the clinics screening eligible participants by appointment date and meeting the potential participants in person to recruit them.

3. Previously consented older cancer survivors in the OSUCCC Total Cancer Care (TCC) registry. The TCC registry, a personalized cancer care initiative designed to collect clinical data and tumor specimens throughout a patient's lifetime, will be utilized to capture a larger cancer populations. TCC's consent rate is 94% of all patients evaluated at the OSUCCC. Based on the eligibility criteria, TCC will contact potential participants, identified across all OSUCCC clinics, through phone calls, to introduce the proposed study and see if they agree to be contacted by the study staff. If permission is given, the study staff member will contact the potential participant and determine eligibility. The study staff member will administer the 10-question RAND-36 Physical Function Subscale (PFSS) to determine physical function limitations. If the participant has at least 1 limitation on the PFSS, the participant will be invited to participate in the study, consented, and invited to the baseline in-person visit. These recruitment procedures will continue for 9 months until 70 older cancer survivors have agreed to participate in the study. Previous efforts by the PI, co-Is, and consultants to recruit older cancer survivors have shown these strategies to be effective.

4. Facebook and Research Match Recruitment Messages. OSU Center for Clinical and Translational Science (CCTS) services will be used to generate advertisements for Facebook and Research Match that align with The Ohio State University's College of Medicine institutional branding standards. Facebook advertisements will use

the following criteria as the target audience: ≥65 years old, geographic location within a 90-minute driving radius of Columbus, Ohio. The Facebook advertisement will direct the user to the E-PROOF Study Search page. These advertisements will be live for a two-week period during recruitment.

Research Match will also be used to recruit potential participants. ResearchMatch is a free and secure online tool created by academic institutions across the country to share study and PI contact information to potentially eligible participants. Potentially eligible participants will receive an email introduction to the study and, if they are interested, permit ResearchMatch to release their contact information to the study team. The research assistant will then contact potential participants, via email or phone, to explain study requirements, and confirm eligibility (≥65 years of age, history of stage 1-3 breast, colorectal, and prostate cancer, completed primary cancer treatment, and have an email address).

5. OSUCCC-James Cancer Program Analytics services will be used to generate a list of OSUCCC patients meeting the study criteria.

Email: Potential participants with email addresses will be emailed an invitation letter, signed by OSUCCC providers, to participate in the study. An informational overview of the study and time commitment will also be provided in the invitation. Potential participants interested in the study will be instructed to contact the Clinical Research Coordinator to discuss any questions and complete the screening questionnaire to confirm eligibility.

B. Recruitment Locations

Recruitment will occur at the Survivorship Clinic and CARE clinics within OSUCCC. Recruitment will occur in the clinic exam rooms and/or the waiting room at these clinics. As noted in the facilities page, OSUCCC is the third largest cancer hospital in the nation. The hospital includes a 36-bed blood and marrow transplant unit, inpatient units in which sub-specialists focus on just one type of cancer, a cancer clinical trials unit, 14 state-of-the-art operating rooms, six interventional radiology suites, special isolation rooms, chemotherapy and transfusion areas, and seven linear accelerators for radiation therapy. The Survivorship Clinic at OSUCCC is one of the country's largest cancer supportive care programs, with about 40 team members. The Cancer and Aging Resiliency (CARE) clinics at OSUCCC provides each older adult with cancer with a comprehensive, multidisciplinary treatment plan. Study team member, [name], is the director of the CARE clinics located at the OSUCCC.

C. Recruitment Follow-up

The research assistant will send out a reminder mailing to all identified participants two weeks after the initial study contact. The research assistant will make at three attempts by phone to reach the non-responders. If no response is given after the third attempt, the potential participant will be considered a "non-responder."

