Follow-up. Three months after the 12-week intervention, all participants will return for an in-person assessment by study staff of physical function, muscle strength, and HRQoL. This information is essential to understanding the sustained impact of this intervention and trajectories of physical function among OCS.

3. *TIMELINE*

We will work with cancer clinic leadership, clinicians, and clinic staff to coordinate recruitment to ensure that clinic flow is not disrupted. The Clinical Research Coordinator, TBN, will serve as a central point of contact and will assist with these activities. Throughout the course of the study period, [name] will hold regular staff meetings to discuss recruitment, and to address any issues that occur on a case-by-case and clinic-by-clinic basis. The Clinical Research Coordinator will directly supervise the day-to-day progress of all study activities. We estimate a large number (n~150) of potentially eligible patients on an average weekday at the OSUCCC, with a limiting factors being workforce, clinic flow, and participation rates. We anticipate that we can feasibly enroll an average of 2 patients per day over 9 months of recruitment and reach our recruitment goal of 70 participants.

Figure 2. Timeline and Work Plan

	Year 1				Year 2			
Study Quarters (over 2 years)	1	2	3	4	1	2	3	4
Participant Recruitment								
Recruitment of 70 older cancer survivors								
Aim 1: Determine Feasibility and Acceptability of Intervention								
Implementation of a 12-week online, tailored nutritional and resistance training counseling intervention								
Measurement of accrual, retention, and adherence rates								
Analysis of participant intervention evaluation								
Aim 2: Examine Efficacy of Intervention								
Measurement of physical function, muscle strength, and height, weight, and waist circumference at baseline and 12 weeks								
Measurement of diet quality, exercise, health-related quality of life, self-efficacy, and demographic and clinical information through REDCap-based questionnaires at baseline and 12 weeks								
Analysis of change in physical function, muscle strength, and height, weight, and waist circumference from baseline to 12 weeks								
Analysis of change in diet quality, exercise, health-related quality of life, self-efficacy, and demographic and clinical information from baseline to 12 weeks								
Examine Maintenance of Intervention								

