Measurement of physical function, muscle strength, and health-related quality of life at 3-month follow-up								
Analysis of change baseline and end-of-study (6 months) in physical function, muscle strength, and health-related quality of life								
Integration and Dissemination Activities								
Project meetings, monitoring, and fidelity checks								
Prepare abstracts, manuscripts, and presentations								
Preparation and submission of next-step grant application								

DATA COLLECTION AND MANAGEMENT PROCESS

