4. DATA TO BE COLLECTED

We are collecting data using all validated measures. Our main outcome is physical function which will be measured by The physical performance assessment, Short Physical Performance Battery (SPPB)⁵⁴, will measure physical function at baseline, end-of-study, and follow-up. The SPPB includes three lower extremity physical performance measures (standing balance, five consecutive chair rises, 4-meter gait walk at usual pace) to assess lower extremity strength.

Secondary outcomes will be:

- *Acceptability.* At end-of-study, intervention group participants will complete a 5-item, Likert-scale questionnaire, with written comments, regarding their preferences for receiving education and counseling, successes and challenges, program satisfaction, and suggestions for improvement.
- *Feasibility.* Intervention feasibility will be measured by rates of accrual, retention, and adherence at baseline, end-of-study, and 3-month follow-up. Recruitment rate is based on Consolidated Standards of Reporting Trials criteria⁵⁵ that includes eligible consented individuals and eligible non-consented individuals with non-recruitment reasons documented. Process information (number/duration of video visits) will be recorded.
- *Muscle Strength.* Handgrip strength will be measured at baseline, end-of-study, and follow-up in both hands using a hydraulic grip strength dynamometer (Jamar Model 7498).
- *Dietary Quality.* Protein intake and dietary quality will be assessed at baseline and end-of-study by the National Cancer Institute's DHQIII.⁵⁶
- *Resistance exercise.* Self-reported resistance exercise will be assessed using the revised version of The Godin-Shephard Leisure-Time Exercise Questionnaire (LTEQ) modified to specifically capture self-reported resistance exercise participation.
- *HRQoL.* RAND-36 Health Status Measure⁵⁷ is comprised of 8 subscales assessing multiple aspects of HRQoL. Physical and mental component summaries are created. All scores range from 0-100, with 100 as the highest.
- *Self-efficacy.* Baseline and end-of-study self-efficacy for diet and resistance training will be measured by: "How sure are you that you could do exercises to make your body stronger for 15 minutes, 3 days a week?" and "How sure are you that you could improve your diet?"

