- *Self-regulation.* Baseline and end-of-study self-regulation for diet and exercise will be measured by the 12-item Dietary Self-Regulation Scale⁵⁸ and the 12-item Exercise Self-Regulation Scale⁵⁹.
- *Technology competency.* The 8-item eHealth Literacy Scale (eHEALS)⁶⁰ will measure knowledge, comfort, and perceived skills of engaging in eHealth at baseline and end-of-study. A 5-point Likert scale will be used.
- *Anthropometry.* Body weight, height, and waist circumference will be collected at baseline and end-of-study.
- *Demographic and Clinical Information.* Participants' age, race, ethnicity, gender, education, income, marital status, insurance status, cancer diagnosis, stage at diagnosis, time since diagnosis, treatments received (e.g., chemotherapy, radiation) and comorbidities will be collected at baseline and updated at end-of-study.

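### Aim 2 hypothesises 3-month improvement in three outcomes not measured at 3 months, names no comparator, and the analysis plan does not say which test decides it

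*Combined protocol and SAP*

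**What the plan says.** **Hypothesis (Specific Aims, Aim 2).** The plan states: "Our hypothesis is that intervention participants will experience statistically significant, clinically meaningful improvements in physical function and associated health outcomes". The outcomes listed are physical function, muscle strength, dietary quality, HRQoL, self-efficacy and weight management, and the sentence ends "weight management) after the 12-week dietary and resistance training intervention and at a 3-month post-intervention follow-up". The control arm is not mentioned.

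**Design (section I, Study Design).** The comparison is between arms: "We will examine the intervention effects on physical function and associated health outcomes during the 12-week period between the experimental and control group".

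**3-month visit.** Section III.2 (Follow-up) says "all participants will return for an in-person assessment by study staff of physical function, muscle strength, and HRQoL". The maintenance block of Figure 2 agrees: "Measurement of physical function, muscle strength, and health-related quality of life at 3-month follow-up". Section 5 on data collection lists the same three domains.

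**Schedule of the other three domains (section 4, Data to Be Collected).**
- Diet: "Protein intake and dietary quality will be assessed at baseline and end-of-study".
- Self-efficacy: "Baseline and end-of-study self-efficacy for diet and resistance training will be measured by" two items.
- Weight: "Body weight, height, and waist circumference will be collected at baseline and end-of-study".

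Section 6 places end-of-study at 12 weeks and follow-up three months later.

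**Analysis (section V.2, Aim 2).** The primary outcome is the SPPB and efficacy is to be judged at 12 weeks. The section then lists a repeated-measures ANOVA, a mixed model with a group-by-time interaction over three visits, contrasts within each arm and between arms at end-of-study, post-hoc group comparisons of all collected variables, and paired t or signed-rank tests of change. These are run in two analysis sets. No result is named as the one that answers Aim 2.

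**The concern.** There are two separate problems.

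First, half of the listed domains carry a 3-month claim that the visit schedule cannot support.

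Second, the hypothesis as worded is a within-arm claim, and some of the listed tests match that wording. A within-arm change can come from practice with the test, season, being measured, or regression to the mean. The last is plausible here because eligibility requires at least one reported physical limitation. The control arm is there to remove such shared changes. With the tests unranked, a significant paired result in the intervention arm could be presented as confirming Aim 2 while the randomised comparison shows no difference. The effect sizes are meant to inform later trials, so the error would carry forward.

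The mixed model is spelled out for physical function only. For the other outcomes, the written tests of change are within-arm, and the between-arm comparison is post-hoc at each visit.

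**Working it through.** **1. Outcomes against schedule.**

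| Domain in hypothesis | Baseline and 12 weeks | 3 months |
|---|---|---|
| Physical function (SPPB) | yes | yes |
| Muscle strength (handgrip) | yes | yes |
| HRQoL | yes | yes |
| Dietary quality | yes | no |
| Self-efficacy | yes | no |
| Weight | yes | no |

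Claims: 6 domains × 2 time points = 12, of which 3 have no data. One row of Figure 2 attaches the term end-of-study to 6 months, but its Aim 2 rows and section 6 put the three affected measures at 12 weeks, so that label does not supply the missing data.

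**2. The plan's own sample size.** Inputs from section V.1: effect size d = 0.50, alpha 0.05 one-sided, power 0.80, result 27 per group. The test is not named.

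- One-sample or paired t-test, noncentrality d√n: power is 0.798 at n = 26 and 0.812 at n = 27. The required n is 26.14, rounded up to 27. This reproduces the stated figure.
- Unadjusted two-arm t-test, noncentrality d√(n/2): the required n is 50.15, so 51 per arm. Power is 0.66 with 35 per arm and 0.58 with 28 per arm. The 28 comes from the retention goal of 56/70 split equally.
- Paired test for comparison: 0.89 with 35 and 0.82 with 28.

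A baseline-adjusted two-arm calculation would give about 26 per arm if the baseline-to-follow-up correlation were 0.7. The documents state no correlation, so the match with a paired test is an inference.

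**3. Between-arm contrast of change.** With equal SDs at both visits, d_change = 0.5/√(2(1−r)). The d detectable with 80% power, one-sided 0.05, is 0.600 with 35 per arm and 0.673 with 28. Solving r = 1 − (0.5/d_change)²/2:

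- 35 per arm: r = 1 − (0.5/0.600)²/2 ≈ 0.65
- 28 per arm: r = 1 − (0.5/0.673)²/2 ≈ 0.72

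**4. Illustration of a shared change.** Assumptions not in the documents: no treatment effect, both arms drift by the same amount (in SDs of change), 28 analysed in the intervention arm. The probability that a paired test there shows significant improvement, with noncentrality drift × √28, is:

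| Drift | One-sided 0.05 | Two-sided 0.05 | One-sided 0.05/3 | Two-sided 0.05/3 |
|---|---|---|---|---|
| 0.1 SD | 13% | 8% | 5% | 3% |
| 0.2 SD | 27% | 17–18% (0.175) | 13% | 8% |
| 0.3 SD | 46% | 33% | 27% | 19% |

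The 0.05/3 columns apply a Bonferroni correction over the three within-arm phase contrasts. Under the same shared drift, a between-arm t-test rejected in 4.8–5.1% of 40,000 simulated trials.

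**The case against.** The strongest reply is that the operative text is sounder than the hypothesis sentence. Figure 2 confines Aim 2 measurement to baseline and 12 weeks and puts the 3-month visit in a separate maintenance block with only the three measured domains. No planned analysis relies on missing data. The Study Design paragraph supplies the comparator. Section V.2 fixes the SPPB at 12 weeks, presents the mixed model as the way to examine the intervention's effect on change in physical function, and includes a between-arm contrast at end-of-study. The within-arm phase contrasts are described as capturing change patterns, and Bonferroni is applied to them. The hypothesis is never called a success criterion, and this is a pilot of preliminary efficacy.

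Much of that stands, and it narrows the point. The primary outcome is untouched by the schedule gap. A reader inclined to the between-arm reading can find it in the plan. The drift figures depend on chosen inputs and are small at 0.1 SD. The uncorrected columns are relevant only to tests outside the Bonferroni correction, such as the paired tests. The one-sided alpha is stated only for the sample size.

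It does not close the gap. The plan does not choose between the three-visit interaction, which is not a 12-week test, and the 12-week contrast, and it does not place either above the paired tests. The hypothesis, which does speak of statistical significance, matches the within-arm tests.

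**Conclusion.** The concern holds. Three of 12 outcome-by-time claims (three of six domains, 3-month visit only) cannot be tested. This follows from the schedule alone and needs no assumption. The Aim 2 hypothesis has no comparator, and section V.2 does not say which of its tests answers it, although outcome and time point are fixed for the SPPB.

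The practical size of the second problem is the gap between tests. At d = 0.50, one-sided 0.05 and 35 per arm, power is 0.89 for within-arm change and 0.66 for an unadjusted between-arm comparison. These figures apply the same 0.50 to both tests, because section V.1 does not say which difference it describes. The false-success rates are illustrative only, since the shared drift is assumed.

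This should be corrected before analysis. It does not prevent the trial from running.

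**What to change.** 1. **Specific Aims, Aim 2:** limit the 3-month hypothesis to SPPB, handgrip and HRQoL, and word the 12-week hypothesis as greater improvement than enhanced control. Measuring weight, waist and the two self-efficacy items at the existing 3-month visit is an optional alternative for those domains. Dietary quality would still be claimed at 12 weeks only.
2. **Section V.2:** name the between-arm contrast of change from baseline to 12 weeks, from the mixed model, as the test that decides Aim 2 for the SPPB. Use the same contrast for each secondary outcome. Report within-arm contrasts and paired tests as descriptive.
3. **Section V.1:** restate power for that contrast and give the assumed baseline-to-12-week SPPB correlation.

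The required changes are to text only, with no added visit or participant. The optional measures would add some time to the 3-month visit. The cost is a less favourable power statement and probably fewer significant results: 80% one-sided power needs a correlation of about 0.65 with 35 per arm, or about 0.72 with 28. If that cannot be supported, the plan should give the lower power and present Aim 2 as estimation with confidence intervals.
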